17.1.3 Targeted Medical Events (TMEs)

Targeted treatment-emergent adverse events will be separately tabulated and labeled as “targeted medical events”. Categories of TMEs will include the following:

- Cardiac
 - Bradycardia
 - AV conduction delay
 - Hypertension
- Macular edema
- Infections
 - Serious infections
 - Opportunistic infection
 - Herpes simplex and herpes zoster infection
- Liver
 - Elevated aspartate aminotransferase (AST)
 - Elevated alanine aminotransferase (ALT)
 - Elevated bilirubin
- Malignancies
- Posterior reversible encephalopathy syndrome (PRES)
- Pulmonary disorders with preferred terms indicating airflow obstruction
- Pulmonary disorders with preferred terms indicating decreased gas exchange

See [Section 27](#) (Appendix VI) for MedDRA terms specifying the identification of Targeted Medical Events (TMEs).

17.2 Laboratory Data

Where data transformation is needed, all available significant digits will be retained prior to populating ADaM dataset(s) with production lab data values.

17.2.1 eGFR

For participants contributing age, sex, and race demographic information, estimated glomerular flow rate (mL/min/1.73m²) will be calculated from serum creatinine using the 2021 update to the CKD-EPI formula ³:

$$\text{eGFR} = 141 * \frac{\left(\min \left(\frac{\text{SCR (mg/dL)}}{\kappa}, 1 \right) \right)^{\alpha}}{\left(\max \left(\frac{\text{SCR (mg/dL)}}{\kappa}, 1 \right) \right)^{1.209}} * 0.993^{\text{AGE}} * X * Y$$

where

$\kappa = 0.7$ for females, 0.9 for males

$\alpha = -0.329$ for females, -0.411 for males

$X = 1.018$ for females, 1.0 for males

$Y = 1.159$ for Black/African-American, 1.0 otherwise

Serum creatinine expressed in $\mu\text{mol/L}$ (SI units) will be converted to mg/dL prior to application of the CKD-EPI formula. Missing serum creatinine will result in missing eGFR value(s).

Participants not contributing any one of age, sex, or race will have eGFR set to missing for all visits. Per-participant eGFR normal range will be determined by passing the relevant central lab serum creatinine normal range through the CKD-EPI formula. It is noted that the threshold for 'High' levels of serum creatinine will be mapped to a 'Low' threshold of eGFR, and the threshold for 'Low' levels of serum creatinine will be mapped to a 'High' threshold of eGFR. Lab values will be flagged as low, normal, or high on the basis of these calculated values, and these flags will be used in tabulations (as opposed to eGFR flags embedded in lab data transferred from central labs). Calculated eGFR will be included in lab data listings and differences between central lab eGFR flags and calculated eGFR flags, if any, will be highlighted in the listings.

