5.1 Inclusion Criteria

Participants must meet ALL of the following inclusion criteria to be eligible for enrollment into the study:

1. Men or women, 18 to 80 years of age, inclusive, at the time of consent
2. Capable of giving signed informed consent, which includes compliance with the requirements and restrictions listed in the Informed Consent Form (ICF)

Disease-Specific

3. Diagnosed with UC ≥ 3 months prior to Screening. The diagnosis of UC must be confirmed by endoscopic and histologic evidence. The endoscopy and histology report should be present in the source documents; however, if not available, the Screening endoscopy and histology may serve as such.
4. Active UC confirmed by endoscopy with ≥ 10 cm rectal involvement. Participants with proctitis only at baseline who meet the other eligibility criteria for inclusion, including the endoscopic and RB criteria for moderate to severe disease, will be capped at 10% of the total participants enrolled.
5. Moderately to severely active UC, defined as an MMS of 5 to 9, including an ES ≥ 2 and an RB subscore ≥ 1
6. Surveillance colonoscopy (performed according to local standard) within 12 months before baseline to rule out dysplasia in participants with pancolitis > 8 years duration or participants with left-sided colitis > 12 years duration. Participants without a surveillance colonoscopy within the prior 12 months will have a colonoscopy at Screening (ie, in place of Screening proctosigmoidoscopy). Any adenomatous polyps must be removed per local standard of care prior to the first dose of study drug.

Prior Treatment Failure

7. Demonstrated inadequate response to, loss of response to, or intolerance to at least 1 of the following therapies:
 - a. Conventional therapy:
 - i. Oral 5-ASA compounds
 - ii. Corticosteroids
 - iii. Thiopurines (eg, AZA or 6-MP)
 - b. Biologic therapy or JAK inhibitor therapy:
 - i. Anti-tumor necrosis factor alpha (TNF α) antibodies (eg, infliximab, adalimumab, or golimumab)
 - ii. Anti-interleukin (anti-IL)12/23 (eg, ustekinumab)

- iii. Anti-integrin antibodies (eg, vedolizumab)
- iv. JAK inhibitors (eg, tofacitinib, upadacitinib)

Note: The medication used to qualify the participant for entry into this category of biologic therapy or JAK inhibitor therapy must be approved for the treatment of UC in the country of use.

General Safety

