- 8. Adequate hepatic function, defined as a total bilirubin level of $\leq 1.5 \times$ upper limit of normal (ULN) and aspartate aminotransferase (AST) and alanine aminotransferase (ALT) levels of $\leq 2.0 \times$ ULN. Participants with Gilbert's syndrome who have an isolated total bilirubin and normal AST and ALT levels may participate.
- 9. Adequate renal function, defined as an estimated glomerular filtration rate ≥ 60 mL/min/1.73 m² by the Chronic Kidney Disease Epidemiology Collaboration equation at Screening

Concomitant Medications

- 10. Participants are permitted to receive the following concomitant medications:
 - a. Oral 5-ASA compounds at a stable dose or discontinued for ≥ 2 weeks prior to Screening endoscopy
 - b. Oral corticosteroid therapy at a stable dose or discontinued for ≥ 2 weeks prior to Screening endoscopy (prednisone at a stable dose ≤ 20 mg/day, budesonide at a stable dose ≤ 9 mg/day)
 - c. Probiotics, provided the dose has been stable for ≥ 2 weeks prior to Screening endoscopy

Contraception

- 11. Women must meet either a or b of the following criteria and men must meet criterion c to qualify for the study:
 - a. A woman who is not of childbearing potential must meet 1 of the following:
 - i. Postmenopausal, defined as no menses for 12 months without an alternative medical cause
 - ii. Permanent sterilization procedure, such as hysterectomy, bilateral salpingectomy, or bilateral oophorectomy
 - b. A nonpregnant woman of childbearing potential must agree to use a highly effective contraception method that can achieve a failure rate of less than 1% per year when used consistently and correctly. The highly effective contraception must be used through the duration of the study and for 30 days after the last dose of study treatment. The following are considered highly effective birth control methods:
 - i. Combined (estrogen- and progesterone-containing) hormonal contraception associated with inhibition of ovulation, which may be oral, intravaginal, or transdermal.
 - ii. Progesterone-only hormonal contraception associated with inhibition of ovulation, which may be oral, injected, or implanted

- iii. Intrauterine device
 - iv. Intrauterine hormone-releasing system
 - v. Bilateral tubal occlusion
 - vi. Vasectomized partner, provided that the partner is the sole sexual partner of the woman of childbearing potential study participant and the vasectomized partner has received medical assessment of the surgical success

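### The eGFR normal range is mapped from the creatinine range, so eGFR Low/Normal/High tables add almost nothing to creatinine and can miss a fall below 60

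*SAP*

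**What the plan says.** SAP 17.2.1 computes eGFR from serum creatinine with a printed formula. It then defines what counts as normal: "Per-participant eGFR normal range will be determined by passing the relevant central lab serum creatinine normal range through the CKD-EPI formula". It acknowledges the reversal, noting that high "levels of serum creatinine will be mapped to a" low eGFR threshold, and the converse for low creatinine. For eGFR these calculated flags displace the laboratory's own: "these flags will be used in tabulations (as opposed to eGFR flags embedded in lab data transferred from central labs". Disagreements between the two sets of flags are highlighted in listings only.

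SAP 17.2.3 plans shift tables of Low, Normal and High flags from baseline to each visit and to the worst post-baseline visit in Induction. They cover all non-normalized assays, and eGFR is named among them. It also plans summaries by visit of values and of change and percent change from baseline. It plans no count or shift at a fixed eGFR value.

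The only eGFR threshold in either document is Protocol 5.1, criterion 9: "Adequate renal function, defined as an estimated glomerular filtration rate" of at least 60 mL/min/1.73 m², at Screening. Entry is open to "Men or women, 18 to 80 years of age, inclusive, at the time of consent".

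**The concern.** A categorical eGFR table is useful if it shows something the creatinine table does not: the same creatinine value means a lower filtration rate in an older person. If the limit is obtained by putting the creatinine limit through the same formula at the same age, age enters the value and the limit alike and drops out of the flag. The table then carries the creatinine information under reversed labels.

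The second consequence concerns older participants. The mapped lower limit falls with age, and nothing keeps it above 60. If it is below 60, a participant who met the entry criterion and later fell under that value would appear in the shift table as unchanged. At stake is how visible renal change is in the safety tables. No efficacy result is involved.

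**Working it through.** The documents state no eGFR limits, so there is no planned figure to reproduce.

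**Inputs from SAP 17.2.1.** eGFR = 141 × min(S/κ, 1)^α ÷ max(S/κ, 1)^1.209 × 0.993^age × X × Y, where S is serum creatinine in mg/dL.
- κ = 0.7 "for females, 0.9 for males"
- α = −0.329 "for females, -0.411 for males"
- X = 1.018 for women and 1.0 for men
- Y = 1.159 "for Black/African-American, 1.0 otherwise"

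**Assumption.** The creatinine upper limit of normal (ULN) is not given. The range used is 1.1 to 1.4 mg/dL for men and 0.9 to 1.2 mg/dL for women.

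**Step 1: redundancy.** Below κ, S carries a negative exponent; above κ it is in the denominator. A grid check from 0.2 to 5 mg/dL, ages 18 to 80, both sexes and both values of Y, confirmed that eGFR falls strictly with S. Hence eGFR < eGFR(ULN) exactly when S > ULN, and likewise at the other end. This holds whatever the laboratory's limits are. In 200,000 simulated values, with the same age used for value and range, the eGFR flags and the reversed creatinine flags never disagreed. That simulation assumed ranges of 0.5–1.0 mg/dL for women and 0.7–1.3 for men. If the range is held at baseline age and the value uses an age one year later, 1.7% disagree.

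**Step 2: creatinine at which eGFR = 60.** For S above κ, S₆₀ = κ × (141 × 0.993^age × X × Y ÷ 60)^(1/1.209). At age 80, 0.993^80 = 0.570.
- Men, Y = 1.0: 0.9 × (141 × 0.570 ÷ 60)^(1/1.209) = 0.9 × 1.340^0.827 ≈ 1.15 mg/dL
- Women, Y = 1.0: 0.7 × (1.340 × 1.018)^0.827 ≈ 0.905 mg/dL
- With Y = 1.159: about 1.296 mg/dL (men) and 1.023 mg/dL (women)

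A ULN above these values puts the mapped lower limit below 60 at age 80. At age 70 with Y = 1.0 the values are 1.215 and 0.959; at age 60, 1.288 and 1.017.

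**Step 3: mapped lower limit of eGFR, Y = 1.0.**

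| Sex, assumed ULN (mg/dL) | Age 60 | Age 70 | Age 80 | Youngest age with limit < 60 | Same, Y = 1.159 |
|---|---|---|---|---|---|
| Men 1.1 | 72.6 | 67.7 | 63.1 | none by 80 | none by 80 |
| Men 1.2 | 65.3 | 60.9 | 56.8 | 73 | none by 80 |
| Men 1.3 | 59.3 | 55.3 | 51.5 | 59 | 80 |
| Men 1.4 | 54.2 | 50.5 | 47.1 | 46 | 67 |
| Women 0.9 | 69.5 | 64.8 | 60.4 | none by 80 | none by 80 |
| Women 1.0 | 61.2 | 57.0 | 53.2 | 63 | none by 80 |
| Women 1.1 | 54.5 | 50.8 | 47.4 | 47 | 68 |
| Women 1.2 | 49.1 | 45.8 | 42.6 | 32 | 53 |

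**Step 4: an example.** Take a man aged 75, Y = 1.0, assumed ULN 1.3; 0.993^75 = 0.590.
- Creatinine 1.10: 141 ÷ (1.10/0.9)^1.209 × 0.590 ≈ 65
- Creatinine 1.29: 141 ÷ (1.29/0.9)^1.209 × 0.590 ≈ 54
- Mapped lower limit: 141 ÷ (1.30/0.9)^1.209 × 0.590 ≈ 53

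He moves from 65 to 54, and both values are tabulated as Normal.

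**The case against.** The best defence is that little depends on these flags. Sixty is a Screening criterion; the documents set no on-study eGFR limit, and neither the treatment-discontinuation rules (Protocol 7.1) nor the Targeted Medical Events (SAP 17.1.3) contain a renal item. Numeric eGFR is summarised by visit and arm, listings highlight disagreements with the laboratory's flags, and investigators review every laboratory report (Protocol 8.4.8). CTCAE-grade shifts are also planned, although the SAP does not say whether renal measures are graded. The reversal is disclosed and prespecified. All of this stands, and it keeps the point small. However, group summaries do not count individuals who cross 60, and listings are not tables.

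Four stronger readings might be inferred, and the documents do not support them:
- **The eGFR and creatinine tables are identical.** Rounding, age at visit and local-laboratory data, which the shift tables include where possible, allow small differences. So does missing age, sex or race, which sets eGFR to missing. If the laboratory's limits are sex-specific, sex is still reflected in the flag.
- **Values below 60 will be called normal.** This depends on the unknown ULN. At 1.1 mg/dL for men and 0.9 for women, the mapped limit stays above 60 through age 80.
- **A young participant flagged Low above 60 is misclassified.** At age 20 the mapped limit is 86.5 for a man with ULN 1.2, but nothing in the documents says that a lower value is normal at that age.
- **The mapped range must be dropped in favour of a full set of fixed categories.** Cut-offs such as 90 and 30 appear nowhere in the documents.

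**Conclusion.** The point holds as a minor, inexpensive improvement to the safety tables. That the eGFR flags essentially mirror the creatinine flags for central-laboratory data follows from the SAP's own rule and needs no laboratory figure. That a post-baseline fall through 60 can be tabulated Normal-to-Normal is conditional on the creatinine ULN and mainly concerns older participants. With Y = 1.0, the mapped limit first drops below 60 at age 73 for men at an assumed ULN of 1.2 mg/dL and at age 63 for women at 1.0; higher limits bring it earlier. How many participants this would affect cannot be estimated from the documents. The numeric summaries and highlighted listings limit the loss to the categorical display.

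**What to change.** Add to SAP 17.2.3 a table by treatment group giving the count and shift of participants with eGFR of at least 60 at baseline and below 60 afterwards, at each visit and at the worst post-baseline value. Compute it from the numeric eGFR, not from the flags, with the denominator already used for the shift tables (participants with both baseline and post-baseline results). Condition on baseline rather than Screening: SAP 9.5 takes the last value before first dose, and Day 1 chemistry could already be under 60. A fixed cut-off does not depend on either central laboratory's creatinine range.

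The mapped-range flags may stay alongside this table, or be replaced if the SAP states why. The cost is one short SAP addition and one table shell; the data are already being computed.

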17.2.2 Lab Values and Normal Ranges

[REDACTED] For purposes of data analysis, ADAM.ADLB (and any other ADaM datasets with laboratory data) will put a limited number of central lab values and normal ranges on a common footing, with [REDACTED] normal ranges serving as the reference ranges. Local lab data will not be transformed in this way. The analytes subject to normalization are absolute lymphocyte count (ALC), absolute neutrophil count (ANC), and high-specificity c-reactive protein (CRP).

³ <https://reference.medscape.com/calculator/251/egfr-using-ckd-epi-2021-update>

[REDACTED] data for ALC, ANC, and CRP will be mapped to [REDACTED] normal ranges. In some cases age and/or sex may need to be taken into account for a given central laboratory and analyte.

To match the manner in which the two central laboratories handle participant Age, the following rules will be applied during the analyte normalization process:

- [REDACTED] participant Age at collection during Screening / Baseline will be incremented by +1 every 30 Jun
- [REDACTED] participant Age at collection during Screening / Baseline will be incremented by +1 every 01 Jan

These Age rules are specific to the analyte normalization process.

The analyte mapping will be done according to the following formulas and the notation in these formulas suppresses both age and sex demographic characteristics for simplicity:

[REDACTED]

[REDACTED]

[REDACTED]

[REDACTED]

[REDACTED]

[REDACTED]

[REDACTED]

[REDACTED]

[REDACTED]

[REDACTED]

[REDACTED]

[REDACTED]

[REDACTED]

[REDACTED]

[REDACTED]

[REDACTED]

[REDACTED]

[REDACTED]

[REDACTED]

[REDACTED]

[REDACTED]

[REDACTED]

[REDACTED]

[REDACTED]

[REDACTED]

[REDACTED]

[REDACTED]

Transformation

Let X_{OBS} = observed lab value

Let X_{REF} = transformed lab value

- [REDACTED]
[REDACTED]
[REDACTED]
[REDACTED]
[REDACTED]
[REDACTED]
[REDACTED]
[REDACTED]
[REDACTED]
[REDACTED]
- [REDACTED]
[REDACTED]
[REDACTED]
[REDACTED]
[REDACTED]

Flag values for individual lab assays (e.g., ‘low’ vs ‘normal’ vs ‘high’, or ‘Abnormal, clinically significant’ vs ‘Abnormal, not clinically significant’ vs ‘Normal’) will not be altered as a result of mapping lab values and normal ranges. These flag values, as determined by central laboratory, will be used in listings and tables. Composite events relying on multiple cutoff values, such as cases of potential drug-induced liver injury, will also be determined using original central lab values and normal ranges.

17.2.3 Summaries

For tabulation purposes, values below assay validity cutoffs will be set equal (e.g., if 1.112 mmol/L is the assay validity lower bound, a reported value of LDL-C < 1.112 mmol/L is set equal to LDL-C = 1.112 mmol/L prior to rounding) and values above assay validity cutoffs will be set equal (e.g., if 13.9 mmol/L is the assay validity upper bound, a reported value of LDL-C > 13.9 mmol/L is set equal to LDL-C = 13.9 mmol/L prior to rounding).

Four general sets of laboratory data summaries will be prepared: Induction Treatment Period, LTE, OLE, and the entire study. Safety Set will be used for induction treatment summaries and Safety-ET Set for LTE/OLE summaries.

Values, change from baseline, and percent change from baseline will be summarized descriptively, by visit, for each treatment group, and only central laboratory data will be tabulated.

- Summary Tables
 - Summary tabulations will only be prepared for central laboratory data using international system (SI) units
 - The normalized assay results (ALC, ANC, and CRP; see [Sections 17.2.1 and 17.2.2](#)) will be summarized separately from all other assay results and [REDACTED]
 - Fecal calprotectin (FCP) will only be summarized separately for [REDACTED]. [REDACTED] FCP will not be pooled, except for shift table purposes. See [Section 10.5](#) for clinically meaningful cutoffs applicable to FCP, regardless of central laboratory.
 - For the non-normalized assay results other than FCP, eGFR and hematology and serum chemistry data will be considered separately and will each be summarized [REDACTED] Visit windowing will be used to associate laboratory data with study visits – see [Section 9.6 Table 3](#).
- Shift Tables
 - Shift tables will include both central and local laboratory data whenever possible.
 - Normalized assay results (ALC, ANC, and CRP) will be considered only on a pooled basis
 - All non-normalized assay results, including FCP and eGFR, will be presented both separately for each central laboratory and also on a pooled basis
 - Shift tables (number and percentage) from baseline to every post-baseline visit will be presented
 - Shift tables for the change in laboratory results interpretation (e.g., flags such as ‘Normal’ vs ‘Low’ vs ‘High’ or ‘Abnormal, clinically significant’ vs ‘Abnormal, not clinically significant’ vs ‘Normal’) from baseline to every post-baseline visit and worst post-baseline visit in Induction Treatment Period
 - Shift tables for the change in CTCAE toxicity grades (with separate parts for decreased and increased grades and Grade = 0 for normal results) from baseline to every post-baseline visit and worse post-baseline visit in Induction Treatment Period

- The number of participants in a particular treatment group having both baseline and post-baseline results available will be used as the denominator.
- Listings
 - Listings will present data in both conventional (CN) and international system (SI) units
 - Hematology, serum chemistry, urinalysis, coagulation data, and pregnancy test data will be listed and these listings will include both central laboratory and local laboratory data.
 - Laboratory values outside normal limits will be identified in the participant data listings with appropriate flags (e.g., ‘Normal’ vs ‘Low’ vs ‘High’ or ‘Abnormal, clinically significant’ vs ‘Abnormal, not clinically significant’ vs ‘Normal’). Abnormal lab values and CTCAE grades over time will be summarized by number and percentage.

Additionally, the number and percentage of participants meeting the following criteria will be presented by treatment group and visit:

- Elevated ALT or AST levels ($>3 \times \text{ULN}$ and total bilirubin $> 2 \times \text{ULN}$ or international normalized ratio (INR) > 1.5 ; $>5 \times \text{ULN}$ for > 2 weeks and $>8 \times \text{ULN}$).
- ALT or AST $> 8 \times \text{ULN}$
- ALT or AST $> 5 \times \text{ULN}$
- ALT or AST $> 3 \times \text{ULN}$
- ALT or AST $> 3 \times \text{ULN}$ and total bilirubin $> 2 \times \text{ULN}$
- ALT or AST $> 3 \times \text{ULN}$ and INR $> 1.5 \times \text{ULN}$

The denominator will be the number of participants in treatment group with non-missing data at specified visit.

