6.6 Guidance for Hepatic Monitoring

An increase in AST or ALT $> 3 \times$ ULN should be followed by repeat testing within 72 hours of receiving results to confirm the abnormality and determine whether AST or ALT is increasing or decreasing.

Discontinuation of study treatment for abnormal liver function should be considered by the Investigator when a participant meets one of the conditions outlined below or if the Investigator believes that it is in best interest of the participant. See also [Section 7.1](#) for more information.

- ALT or AST $> 8 \times$ ULN
- ALT or AST $> 5 \times$ ULN for > 2 weeks
- ALT or AST $> 3 \times$ ULN and total bilirubin $> 2 \times$ ULN or international normalized ratio (INR) > 1.5
- ALT or AST $> 3 \times$ ULN with the appearance of fatigue, nausea, vomiting, right upper quadrant pain or tenderness, fever, rash, and/or eosinophilia ($> 5\%$)

All events of ALT or AST $> 3 \times$ ULN and total bilirubin $> 2 \times$ ULN ($> 35\%$ direct bilirubin), or ALT or AST $> 3 \times$ ULN and INR > 1.5 , if INR measured, which may indicate severe liver injury (possible Hy's Law), must be reported as an SAE. See [Section 8.5](#) for follow-up and reporting of SAEs.

Because transient fluctuations of ALT or AST are common, and progression to severe drug-induced liver injury or acute liver failure is uncommon, automatic discontinuation of study treatment upon finding a greater than $3 \times$ ULN elevation of ALT or AST may be unnecessary.

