9.6 Windowing Conventions

All scheduled study visits are defined relative to Study Day 1, the date of first Induction Treatment Period dose.

Scheduled visit windows for the Induction Treatment Period are defined in Protocol VTX002-201 Section 1.2 Table 1. Scheduled visit windows for the LTE are defined in Protocol VTX002-201 Section 1.2 Table 2. Scheduled visit windows for the OLE are defined in the Protocol VT002-201 Section 1.2 Tables 3, 4, 5, and 6.

A windowing convention will be used to determine the analysis visit value for a given measurement and will be applicable for all by-visit summaries and analyses for efficacy and safety data. Refer to [Table 3](#) for specific Induction Treatment Period visit windows.

Windowing will be applied prior to any missing data calculations. The last non-missing measurement taken prior to Day 1 (including unscheduled assessments) will be labeled as Baseline. Unless stated otherwise, data from scheduled, unscheduled, and early termination site visits will be eligible for allocation to an analysis visit. Follow-up visit data is handled as-is.

Table 3. Analysis Visit Windows

	Visit Label	Study Week	Ideal Study Day (Study Day)	Protocol Visit Window (Study Day)	Analysis Visit Window (Study Day)
Non-Efficacy, Physician's Global Assessment (PGA), IBDQ ^a	Visit 1/Baseline	n/a	-14	[-28, -1]	≤1
	Visit 2	0	1	[1]	[1, 4]
	Visit 3	1	8	[8, 10]	[5, 18]
	Visit 4	4	29	[26, 32]	[19, 42]
	Visit 5	8	57	[54, 60]	[43, 63]
	Visit 6	10	71	[68, 74]	[64, 81]
	Visit 7	13	92	[89, 95]	[82, 102]
Endoscopy and Colonic Biopsy ^b	Visit 1/Baseline	n/a	-14	[-28, -1]	≤1
	Visit 7	13	92	[89, 95]	[76, 108]
SF and RB calculated from eDiary entries ^{b, c}	see footnote	see footnote	see footnote	see footnote	see footnote
Early Term /Unscheduled ^d	see footnote	see footnote	see footnote	see footnote	see footnote
1-Week Follow-up ^d	1-Week Follow-up	n/a	X+7	n/a	n/a
2-Week Follow-up ^d	2-Week Follow-up	n/a	X+14	n/a	n/a

^a Analysis visit windows and Ideal Study Days are intended to map, to Study Visits, all by-visit data collected during the Induction Treatment Period.

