data from ET and Unscheduled visits not associated with Visit 7 will be listed only. 1-Week and 2-Week Follow-up data is not windowed and presented according to nominal visit label in tables.

For composite scores such as MMS, if one or more components is missing from an analysis visit window the composite score is missing. If one or more results for a variable are assigned to the same analysis visit, the result with the date closest to the protocol Ideal Study Day will be used in the analysis, except for rectal bleeding and stool frequency component subscores used in the determination of Symptomatic Remission, Symptomatic Response, MMS, or total MCS. In this case, 7-day look-back windows anchored to either an endoscopy or a site visit are used to determine the component subscores.

If two measurements in the same analysis visit window are equidistant from the protocol scheduled study day, the earliest measurement will be used in the analysis. If multiple assessments are available on the same day, then the average of the assessment will be used in the analysis, except for laboratory data where the assessment at the earliest time of the same day will be used. Central laboratory assessments will be used in both summaries and listings, while local laboratory assessments will only be separately listed. Local laboratory data may be used by investigators to help inform participant safety decisions and adverse event reporting.

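### The liver-criteria table in SAP 17.2.3 uses one result per visit window, so it can miss off-schedule liver peaks, and its last row uses a different INR cut-off from the protocol

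*SAP*

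**What the plan says.** SAP 17.2.3 lists six liver rows: ALT or AST above 3, 5 and 8 × ULN; ALT or AST above 3 × ULN with bilirubin; the same with INR; and a compound first row that also holds the criterion of more than 5 × ULN for more than 2 weeks. They are introduced by "Additionally, the number and percentage of participants meeting the following criteria will be presented by treatment group and visit". The percentages are also per visit: "The denominator will be the number of participants in treatment group with non-missing data at specified visit". No row counts participants who met a criterion at any time after first dose.

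For laboratory summaries the section says that "Visit windowing will be used to associate laboratory data with study visits" and points to SAP 9.6. There the windowing convention "will be applicable for all by-visit summaries and analyses for efficacy and safety data", and "data from scheduled, unscheduled, and early termination site visits will be eligible for allocation to an analysis visit". Within a window, "the result with the date closest to the protocol Ideal Study Day will be used in the analysis"; that sentence exempts only the rectal bleeding and stool frequency subscores. For two equidistant results, "the earliest measurement will be used in the analysis".

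On INR, the first SAP row uses INR > 1.5 and the last uses INR > 1.5 × ULN. Protocol 6.6, Protocol 7.1 and Appendix 3 (Table 11, footnote b) all use INR > 1.5. Protocol 6.6 describes ALT or AST > 3 × ULN with INR > 1.5 as an event "which may indicate severe liver injury" and requires it to be reported as an SAE.

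**The concern.** The protocol itself generates off-schedule liver samples. Section 6.6 asks for a repeat within 72 hours of receiving an ALT or AST above 3 × ULN, and Table 1 of the Schedule of Activities (footnote q) places an extra coagulation panel at an unscheduled visit when ALT or AST is raised. If a case worsens between visits, these are the samples that show it. A rule that prefers the sample nearest the ideal day takes no account of severity and will often prefer the routine sample.

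The incidence of laboratory abnormalities is a declared safety endpoint (Protocol 3.2, SAP 7.3). The liver table is where the arms would be compared on these thresholds. As written, it could show nobody in a combined row while the trial holds an SAE report of a possible Hy's Law event.

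**Working it through.** **1. Days on which an off-schedule result must lose.** Analysis windows and ideal days are from SAP Table 3; permitted visit days are from Protocol Table 1. For each window, let r be the largest distance from the ideal day that a permitted scheduled draw can have. An off-schedule result on day d is certain to lose when |d − ideal| > r. Days that can only tie are not counted.

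| Visit | Window (days) | Ideal day | Permitted draw | r | Days certain to lose |
|---|---|---|---|---|---|
| Week 1 | 5–18 (14) | 8 | 8–10 | 2 | 5 and 11–18: 1 + 8 = 9 |
| Week 4 | 19–42 (24) | 29 | 26–32 | 3 | 19–25 and 33–42: 7 + 10 = 17 |
| Week 8 | 43–63 (21) | 57 | 54–60 | 3 | 43–53 and 61–63: 11 + 3 = 14 |
| Week 13 | 82–102 (21) | 92 | 82–95 | 10 | none |

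Weeks 1, 4 and 8 together: (9 + 17 + 14) / (14 + 24 + 21) = 40/59 = 68%.

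Week 13 differs because footnote a of Protocol Table 1 lets Visit 7 assessments be done up to 7 days before the visit. A compliant draw can fall on Day 89 − 7 = 82, which is 92 − 82 = 10 days from the ideal day, and no day in 82–102 is further away than that. The Week 10 window (Days 64–81, 18 days) has no scheduled chemistry, so a result there normally has no rival. Over all five windows the figure is 40 / (59 + 18 + 21) = 40/98 = 41%.

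If the scheduled draw is on the ideal day, every other day loses: 13 + 23 + 20 = 56 of 56 other days in the Week 1, 4 and 8 windows.

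**2. A dropped peak (hypothetical values).** The scheduled Day 29 sample shows ALT 4 × ULN and bilirubin 1 × ULN. The repeat on Day 33 shows ALT 9 × ULN and bilirubin 2.5 × ULN. Both lie in 19–42. The distances are 0 and 4, so Day 29 is kept. The participant is counted above 3 × ULN but not above 5 × ULN, above 8 × ULN, or in the ALT-plus-bilirubin row.

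**3. Mixed dates (hypothetical values).** During Induction, coagulation is scheduled only at Screening, Week 13 and early termination. Suppose Day 29 shows ALT 2.8 × ULN, and an unscheduled Day 36 sample shows ALT 6 × ULN with INR 1.7. ALT is taken from Day 29 (distance 0 against 7). INR is taken from Day 36, where it has no rival. The table pairs 2.8 × ULN with INR 1.7 and the combined criterion fails, although the Day 36 pair meets ALT > 3 × ULN with INR > 1.5. ALT and bilirubin belong to the same chemistry panel, so mixing mainly concerns INR.

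**4. Duration.** A single value per visit carries no duration. The ideal days 8, 29, 57 and 92 are 21, 28 and 35 days apart. The values that would show an episode lasting more than 2 weeks between visits are those the rule discards.

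**5. INR cut-off.** The last row requires INR > 1.5 × ULN. The documents give no INR ULN. For an assumed ULN of 1.0, 1.1, 1.2 or 1.3 the cut-off is 1.50, 1.65, 1.80 or 1.95, against 1.5 in the first row and the protocol. They agree only if ULN = 1.0.

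**The case against.** The best defence is that this is one descriptive table in a Phase 2 trial with several back-ups. Possible Hy's Law events must be reported as SAEs, and SAEs are tabulated (SAP 17.1.2). Raised ALT, AST and bilirubin are targeted medical events (17.1.3). Shift tables of flags and CTCAE grades include a worst post-baseline visit, and all results are listed. This stands: the cases are not hidden. It does not replace the missing rows. The shift tables take one analyte at a time and do not say whether the worst value is chosen before windowing, and the adverse-event tables depend on what was reported.

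A second defence is that repeat testing follows a value already above 3 × ULN. When that trigger is the scheduled sample nearest the ideal day, it is kept and counted. This also stands, and it limits the loss to the higher and combined rows in that situation. Likewise, an unscheduled INR before Week 13 usually survives; the difficulty there is its pairing, not its loss.

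Third, SAP 17.2.2 says that composite liver events use original central values and ranges. That settles which values and reference ranges apply, not which dates. SAP 19 refers to a mock-output file for programming detail, and a derivation may be given there; the SAP text does not state one.

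Finally, the first row already carries INR > 1.5, so the INR mismatch is confined to one row. That is correct, but the list then contradicts itself.

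**Conclusion.** Wrong as written. The by-visit table, combined with the nearest-day rule, can undercount liver criteria, can mix dates in the INR combinations and cannot evaluate the duration criterion. The figure of 40 of 59 days counts calendar days, not expected events, and assumes that scheduled draws were taken inside their protocol windows. The size of the INR discrepancy depends on a ULN that the documents do not give.

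A reader might infer more than this. One such reading is that every liver threshold is undercounted; the documents do not support it, because a retained scheduled trigger value still counts above 3 × ULN and Week 10 window results normally survive. Another is that the Week 13 window loses results with the same certainty as the earlier ones; the 7-day allowance for Visit 7 rules that out. A third is that the same fault covers ECG and Day 1 readings; SAP 17.5.1 has its own rule of using the earlier assessment within a timepoint, so the point is not extended to them.

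**What to change.** In SAP 17.2.3:

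- Add rows for each liver criterion met at any time after first dose and make them the main presentation, using all central results (scheduled, unscheduled, early termination) before windowing.
- Assess combined criteria on same-date results, or on results within a stated number of days.
- Derive the criterion of more than 5 × ULN for more than 2 weeks from serial values.
- Keep the by-visit rows as supplementary.
- Reconcile the last INR row with the first row and with the possible Hy's Law definition in Protocol 6.6, so that the table and the SAE rule count the same events. This is a matter of consistency, not a view on which cut-off is clinically right.

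The cost is some SAP wording and one extra derived flag in the laboratory dataset. The downside for the sponsor is that reported incidences may be slightly less favourable.
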